To estimate the treatment effect for longitudinally measured continuous outcomes, the outcome will usually be defined as “change from baseline” (difference at follow-up visit minus baseline value). The treatment effect through follow-up will then be estimated with 95% confidence intervals using generalized estimating equations (GEE) with an indicator for treatment group, or, in the case of Gaussian responses, the corresponding mixed effects models with random effects for participants. When there is more than one follow-up visit, “visit number” (day) may be included as categorical variable in the model, for variance reduction; alternatively, “time” may be included as continuous variable. Models will also be adjusted for the baseline values of the outcome variable.

**Time-to-event outcomes** will be summarized with Kaplan-Meier estimates for cumulative probabilities over time, and compared between treatment groups using log-rank tests or Cox proportional hazards models, or the corresponding competing risk analogues when death is a competing risk for the outcome. In particular, the primary endpoint of “time to sustained recovery” will be analyzed taking into account the competing risk of death. The following competing risk methods will be used:

- Aalen-Johansen estimator for the cumulative incidence function (analogue to the Kaplan-Meier estimate)
- Gray’s test with  $\rho=0$  (analogue to the log-rank test)
- Fine-Gray estimates and tests for the sub-distribution hazard ratio (analogue to the Cox proportional hazards model).

The proportional hazards assumption will be tested by adding an interaction term for time by treatment group to the model. The cumulative proportions of participants who experienced the event will also be compared at given time points (specified in secondary objectives, e.g., at 28 days); in this case, the cumulative proportions will be estimated using Kaplan-Meier estimates or the competing risks analogue, and/or as proportion of participants who reached the time point (e.g., time since randomization  $\geq 28$  days).

The **administrative follow-up time** is defined as the minimum of (cut date minus randomization date) or the analysis time period. For example, the analysis time period for the primary endpoint of *sustained recovery* is 90 days, and the analysis time period for the important safety endpoint, the composite of *grade 3 and 4 events, SAEs, organ failure, serious*

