- Treatment groups will be compared for the proportion of participants who developed *organ failure or serious infections* through Day 28 and through Day 90, overall and by individual components, using stratified CMH tests. Individual components of this composite outcome will be tabulated.
- Treatment groups will be compared for incidence of organ failure, serious infections, or death through Day 28 and through Day 90, using Cox proportional hazards models; cumulative incidence functions will be estimated using Kaplan-Meier estimates.
- Treatment groups will be compared for incidence of a composite of fatal and non-fatal cardiovascular and thromboembolic events, a subset of the organ failure outcome (items 6b1, 6e2, 6e3, and 6f2 in [Appendix B](#)). Treatment groups will be compared using Cox proportional hazards models; cumulative proportions of participants with such events will be estimated using Kaplan-Meier estimates.

**Comment:** Death for causes other than cardiovascular or thromboembolic events is a competing risk. As sensitivity analysis, the treatment groups will be compared using Aalen-Johansen estimates for the cumulative incidence functions and Fine-Gray models to estimate the sub-hazard ratio (investigational agent versus placebo) for the composite outcome. If results differ substantially from the Cox regression and Kaplan-Meier estimates, mortality for reasons other than CVD and thromboembolic events will be investigated in detail.

- Treatment groups will be compared for **new requirements of dialysis**, overall and in subgroups by eGFR level (<30 mL/min versus  $\geq$ 30 mL/min at study entry), and subgroups by nAb status at study entry (nAb negative or positive).

**Motivation:** In a joint analysis of data from the first three agents studied in TICO (bamlanivimab, sotrovimab, and BRII 196/198), the incidence of dialysis was elevated in the active treatment group compared with placebo (18 versus 2 events, HR=5.7 [95% CI: 1.2-24.6]). This safety signal was seen only among those who were nAb seronegative at study entry (16 events in the active arms versus 2 placebo, HR=5.0 [95% CI: 1.1 to 22.0]),

while only 2 events occurred among those who were nAb seropositive at study entry, both in the active arms. The mean time from enrollment to needing dialysis was 21 days.

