Additionally, the ordinal outcomes will be dichotomized (“category 1”, “best 2 categories” through “best 5 categories”), and proportions will be compared between treatment groups at selected time points using logistic regression. For these analyses, the key dichotomized outcome considers the “best 2 categories”, which is similar to the “recovery” outcome in the ACTT-1 trial.

- *Clinical organ failure or serious infections*, defined by development of any one or more of the clinical events listed in [Appendix B](#), through Days 28 and 90. The development of *organ failure or serious infections* will be analyzed as a binary outcome, and the proportions of participants who developed *organ failure, serious infections or death* will be compared across arms using stratified CMH tests, overall and for individual components.
- A composite of death, clinical organ failure, or serious infection through Days 28 and 90 (see [Appendix B](#)). Treatment groups will be compared using standard time-to-event methods, since death is part of the outcome and not a competing risk. (Also described in section 7 as safety analysis).
- Outcomes assessed in other treatment trials of COVID-19 for hospitalized participants in order to facilitate cross-trial comparisons and overviews (e.g. 6-, 7-, and 8-category ordinal scales assessed at Days 1-7, 14 and 28; time to improvement in 1 or 2 categories of ordinal scale; time to best 3 categories of ordinal scale, and binary outcomes defined by improvement or worsening based on other ordinal outcomes). We will try to match the analyses in the other trials, to get results that can be compared. These analyses will not be performed for interim reports to the DSMB, unless requested.
- A composite of cardiovascular events (outcomes listed in items b1, e2 and e3 in [Appendix B](#)) and thromboembolic events (item f2). Time to event methods will be used that take into account the competing risk of death, e.g., Gray's test to compare treatment groups.

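### SAP sections 7 and 8.3 analyse the same cardiovascular/thromboembolic composite with different main methods, leave some cardiovascular deaths unclassified, and do not say which analysis governs

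*SAP*

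**What the plan says.** **SAP section 7** (safety) states: "Treatment groups will be compared for incidence of a composite of fatal and non-fatal cardiovascular and thromboembolic events, a subset of the organ failure outcome". It ties this composite to "items 6b1, 6e2, 6e3, and 6f2 in" Appendix B. Without the leading 6, which Appendix B of the SAP does not use, these are myocardial infarction (b1), cerebrovascular event (e2), transient ischaemic event (e3) and arterial or venous thromboembolism (f2). The main analysis is: "Treatment groups will be compared using Cox proportional hazards models; cumulative proportions of participants with such events will be estimated using Kaplan-Meier estimates". A comment then adds: "Death for causes other than cardiovascular or thromboembolic events is a competing risk". The sensitivity analysis compares the groups "using Aalen-Johansen estimates for the cumulative incidence functions and Fine-Gray models to estimate the sub-hazard ratio". If the two sets of results differ substantially, mortality from other causes is to be examined.

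**SAP section 8.3** (other secondary outcomes) lists a composite of the same four items. It does not mention fatal events. The method is: "Time to event methods will be used that take into account the competing risk of death, e.g., Gray's test to compare treatment groups".

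**SAP section 3**, in the paragraph on time-to-event outcomes, sets the general rule: Kaplan-Meier, log-rank and Cox, "or the corresponding competing risk analogues when death is a competing risk for the outcome".

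**The concern.** One composite appears twice, and the approach that is main in one place is only a sensitivity analysis in the other. The neighbouring composite in section 8.3 (death, organ failure or serious infection) is cross-referenced to section 7; this one is not.

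Three things are at stake:

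- **Event definition.** Section 7 says which deaths compete and that fatal events count. Section 8.3 is silent on fatal events and does not restrict the competing deaths by cause. Two programmers could each follow the SAP and classify the same participant differently.
- **Cumulative proportions.** Section 7 recognises a competing risk but still makes Kaplan-Meier its main estimate. With competing deaths censored, one minus Kaplan-Meier estimates what would be seen if those deaths did not occur, and so overstates the proportion who actually have the event.
- **Choice of result.** If the Cox and Gray results point in different directions, the SAP does not say which is the main comparison.

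**Working it through.** The documents give no event count, rate or power for this composite, so there is no plan figure to reproduce.

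**Step 1. The two sections side by side**

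| | Section 7 | Section 8.3 |
|---|---|---|
| Items | b1, e2, e3, f2 | b1, e2, e3, f2 |
| Fatal events | Counted | Not mentioned |
| Competing deaths | Other causes only | Death, cause not restricted |
| Main method | Cox and Kaplan-Meier | Competing-risk methods, Gray's test as the example |
| Sensitivity method | Aalen-Johansen, Fine-Gray | None stated for this outcome |
| Default cohort | mITT | ITT |
| Time horizon | None stated | None stated |

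**Step 2. Three participants coded under each section**

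- *Fatal myocardial infarction recorded under b1.* With ordinary first-event coding, this is an event in both.
- *Death from respiratory failure, no item event.* A competing death in both.
- *Death from heart failure, no item event.* Heart failure is Appendix B item b3, which is not in the composite. Under section 7 the cause is cardiovascular, so the comment does not make it a competing death. It is then either an event (reading fatal cardiovascular events broadly) or unclassified (reading the four-item list strictly). Under the plain wording of section 8.3 it is not an item event, so it is a competing death.

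The conflict is therefore confined to cardiovascular or thromboembolic deaths with no recorded item event. Their number is not in the documents. Table E-1 gives 138 deaths before recovery among 1417 infused in the AZD7442 trial (138/1417 = 9.7%), with no breakdown by cause. An assumed share of 0-20% gives 0 to 138 × 0.20 = 27.6 deaths. That range starts at zero and rests entirely on the assumed share.

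**Step 3. Kaplan-Meier against Aalen-Johansen**

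Assumptions: true cumulative incidence p of the composite 3-10%; competing death m 5-15%, with 9.7% as the middle value (a proxy, because it covers deaths of all causes); constant cause-specific hazards over the period.

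- Total cumulative hazard: H = −ln(1 − p − m)
- Composite share: h = H × p/(p + m)
- One minus Kaplan-Meier: 1 − exp(−h)

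For p = 5% and m = 9.74%: H = −ln(0.8526) = 0.1595; h = 0.1595 × 0.05/0.1474 = 0.0541; 1 − exp(−0.0541) = 5.27%. The excess is 0.27 percentage points.

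| True incidence p | m = 5% | m = 9.7% | m = 15% |
|---|---|---|---|
| 3% | 3.08% | 3.16% | 3.25% |
| 5% | 5.13% | 5.27% | 5.43% |
| 10% | 10.27% | 10.54% | 10.87% |

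The excess runs from 0.08 to 0.87 percentage points, or 2.6% to 8.7% in relative terms. It depends on timing. It is zero if all competing deaths follow the events. If they all come first, it is p/(1 − m) − p, which in the middle case is 0.05/0.9026 − 0.05 = 0.54 points.

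**Step 4. Cause-specific against subdistribution ratio**

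Take control-arm p = 5% and m = 9.74%, and a cause-specific hazard ratio of 1.5 for the composite. Approximate the subdistribution ratio by ln(1 − CIF active)/ln(1 − CIF control). It is 1.52 if the agent's hazard ratio for other death is 0.7, 1.50 at 1.0 and 1.47 at 1.4. In this setting the choice between Cox and Fine-Gray moves the estimate little.

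**The case against.** **Section 7 already deals with the competing risk.** It names it, plans Aalen-Johansen and Fine-Gray, and says what follows if results differ. This stands: the overstatement would be visible in the report. What remains is that the less suitable estimate is the main one, against section 3.

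**Cox with other-cause deaths censored is legitimate.** It estimates a cause-specific hazard ratio, a recognised safety measure. This stands, and it is a reason to keep the Cox model.

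**Readers might infer more than the text supports:**

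- *That cardiovascular deaths are events in section 7 and competing in section 8.3.* Section 8.3 does not say so; it is one reading of an unrestricted reference to death. A fatal infarction or stroke can be a b1 or e2 event in both. Section 7 can also be read as limited to fatal and non-fatal instances of the four items.
- *That two different event counts, or a fatal signal seen in one analysis only, must follow.* This needs one particular reading of each section, plus a composite rate, a share of deaths and an effect on cardiovascular death that the documents do not give.
- *That there are two headline results.* One is a supportive safety analysis and the other is an other secondary outcome. No alpha or decision rule is attached to either in the SAP.
- *That the cohorts conflict throughout.* The mITT/ITT difference is only the platform default. Appendices E and G set mITT for efficacy and safety for AZD7442 and MP0420, and section 3 has populations reconsidered before unblinding.

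**The master protocol may settle the definition.** Section 8.3 draws its outcomes from protocol section 4.2.2, which is not among the documents supplied. This stands and shapes the fix.

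**Conclusion.** The inconsistency is real but modest. The same four-item composite has different main methods in two sections, with no hierarchy, cross-reference or time horizon. The handling of fatal events is stated in section 7 and left open in section 8.3. A cardiovascular or thromboembolic death without an item event can be coded differently in the two analyses, at an unknown frequency that could be zero.

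The part with a demonstrable direction is the Kaplan-Meier proportion, which exceeds the cumulative incidence by roughly 0.1 to 0.9 points. That size rests on assumed event and death rates and constant hazards; only the 9.7% middle value comes from the documents, and it comes from one agent's pooled data. The difference between the ratio measures is smaller still in the illustration. Nothing here affects the primary endpoint.

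**What to change.** 1. **One definition, used in both sections.** State whether a cardiovascular or thromboembolic death with no prior b1, e2, e3 or f2 event is an event or a competing event, and that all other deaths compete. Align this with protocol section 4.2.2, so that the SAP does not widen the endpoint by accident. Give the time horizon in the same sentence.
2. **Cumulative proportions in section 7.** Make Aalen-Johansen the main estimate in place of Kaplan-Meier, in line with sections 3 and 8.3.
3. **Group comparison.** Keep the Cox model, labelled as a cause-specific hazard ratio, alongside Gray's test and Fine-Gray, and state which is the main comparison.
4. **Section 8.3.** Replace the method sentence with a reference to the section 7 definition and analysis.
5. **Cohort.** For agents on the platform default, name mITT or ITT as main for this outcome. AZD7442 and MP0420 need no change.

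The cost is SAP wording before unblinding. Cause of death is already MedDRA-coded, and the competing-risk analyses are already planned as sensitivity analyses. The downside is some subjectivity in assigning cause of death, which section 7 already accepts by separating other-cause deaths.

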## 8 Efficacy Analyses

**Analysis cohort:** Comparisons between each investigational agent and its concurrently randomized (pooled) controls will be by intention-to-treat (ITT) unless otherwise stated.

### 8.1 Primary Efficacy Endpoint and Primary Analysis

The **primary efficacy outcome** of the trial is “time from randomization to *sustained recovery* through Day 90”. *Sustained recovery* is defined as being discharged from the index hospitalization, followed by being alive and *home* for 14 consecutive days.

**Comment:** The shortest possible time to sustained recovery is 14 days (this would require the patient to be discharged from the hospital on the day of randomization), and a patient would have to be discharged from the index hospitalization no later than Day 76 to achieve *sustained recovery* by Day 90.

#### Definition of *Home* for the primary endpoint:

According to the protocol, section 4.2, *Home* is defined as the level of residence or facility where the participant was residing prior to hospital admission leading to enrollment in this protocol.

Residence or facility groupings to define home are:

- 1) **Independent/community dwelling** with or without help, including house, apartment, undomiciled/homeless, shelter, or hotel
- 2) **Residential care facility** (e.g., assisted living facility, group home, other non-medical institutional setting)
- 3) **Other healthcare facility** (e.g., skilled nursing facility, acute rehab facility)
- 4) **Long-term acute care hospital** (hospital aimed at providing intensive, longer term acute care services, often for more than 28 days).

Lower (less intensive) level of residence or facility will also be considered as home. By definition, “home” cannot be a “short-term acute care” facility. Participants previously affiliated with a “long-term acute care” hospital recover when they return to the same or lower level of care.

Readmission from “home” (to a higher level of care) may occur and if this occurs within 14 days of the first discharge to “home”, then the primary endpoint will not be reached until such time as the participant has been at home for 14 consecutive days.

Participants residing in a facility solely for public health or quarantine purposes will be considered as residing in the lowest level of required residence had these public health measures not been instated.

#### Primary analysis

The investigational agent will be compared to the (pooled) control group for *time to sustained recovery through Day 90* by intention-to-treat, using Gray’s test with  $\rho=0$ . The test will be

stratified by disease severity at entry and by site pharmacy (as described in section 3 under “stratification”). Gray’s test compares the cumulative incidence functions for *sustained recovery* between the treatment groups, taking into account the “competing risk” of death in analyzing *sustained recovery*. Gray’s test with  $p=0$  is the competing-risks analogue of the log-rank test.

**Comments:**

1. Comparisons will be presented such that recovery rate ratios (RRR)  $>1$  denote superiority of the investigational agent.
2. For AZD7442, the primary analysis is hierarchical: the overall comparison between treatment groups is followed by a comparison within the subgroup of participants who are nAb seronegative at study entry (described in [Appendix E](#)).

Analyses for the *sustained recovery* endpoint require methods that take into account the competing risk of death, as participants may die before ever achieving *sustained recovery*. The *sustained recovery* outcome requires knowledge of a participant’s residence status for at least 14 days after arriving “home” (as defined above).

- The cumulative incidence functions for sustained recovery will be estimated by treatment group, using Aalen-Johansen estimators. The estimates will be plotted over time, and tabulated at selected time points (days 15, 21, 28, 42, 60, 75, 90). The Aalen-Johansen estimator for a cumulative incidence function is the analogue of the Kaplan-Meier estimator in the presence of competing risks.
- The recovery rate ratio (RRR) for time to sustained recovery of the investigational agent versus control will be estimated, as a point estimate with a 95% CI, using the Fine-Gray model, stratified by disease severity at study entry and study site pharmacy. The corresponding p-value for RRR=1 versus the two-sided alternative will be calculated. The Fine-Gray method is the competing risks equivalent of Cox proportional hazards models; the RRR compares the cumulative incidence rates of *sustained recovery* between the study arms and is a sub-distribution hazards ratio (sHR).
- To aid in the interpretation of the estimated treatment difference, the median days to sustained recovery (through Day 90) will be estimated for the investigational agent and the control group. Medians will be compared using the Wilcoxon rank sum test or quantile (median) regression. Participants who die at any time up to Day 90 will be assigned 91 days.

**Censoring:**

- Participants who are alive but have not experienced sustained recovery will be censored at the last date the endpoint status was ascertained (for interim analyses as well as the final analysis).
- For interim monitoring, two sensitivity analyses will be performed:
  1. Follow-up for time to sustained recovery will be censored *administratively* at the cut-date for the current report or Day 90, whichever comes first, with last known endpoint status carried forward. For participants who died, this type of censoring is integrated into Gray’s test; using a log-rank test would require carrying forward the “not recovered” status for participants who died, up to the administrative censoring date.

2. Administrative censoring as described above will be applied, with the modification that participants who have been discharged from the hospital, were “home” at the latest date when residence was ascertained (but for < 14 days), and, if they have remained there, would have been at home for 14+ days by the cut-date, will be imputed as having experienced *sustained recovery* (achieved on day 14 at home).

Participants who withdrew consent or were lost to follow-up will be censored at the date of withdrawal or the last date the endpoint status was known, respectively.

In the first sensitivity analysis, the “not recovered” status is carried forward to the administrative censoring date; in the second analysis, “sustained recovery” is assumed at the earliest possible date. The first analysis potentially underestimates the rate of recovery, whereas the second analysis overestimates the recovery rate. In all analyses for time to sustained recovery, death is treated as competing risk.

### **Ascertainment of sustained recovery**

The date of discharge from the index hospital will be recorded. Irrespective of the timing of the hospital discharge, there will be patient contact approximately every two weeks, on Days 14, 28, 42, 60, 75, and 90, either at a scheduled clinic visit or through phone contact. At these time points, a) vital status, and b) the location of the participant over time will be recorded, to assess whether the participant had been “at home” for 14 days. Therefore, the outcome status of sustained recovery will usually be ascertained within 3 weeks or less of the date the outcome was achieved.

- To illustrate the status of the primary endpoint, the recovery status of participants will be described over time with the following categories (at interim reviews):
  1. At home for 14+ days (reached the primary endpoint of sustained recovery)  
*Did not reach sustained recovery, and:*
  2. At home, < 14 days
  3. Discharged from the hospital, but not at home
  4. Hospitalized
  5. Dead
  6. Primary endpoint status unknown.

The proportions of participants in each of the 6 categories will be summarized over time, by treatment group (stacked bar graphs and tables). In this analysis, both “sustained recovery” and “death” are absorbing states.

